## Glossary of Abbreviations

ACGME	Accreditation Council for Graduate Medical Education
CCC	Continuous curvilinear capsulorrhexis
ECCE	Extracapsular cataract extraction
FRCOphth	Fellow of the Royal College of Ophthalmologists (UK)
FVR	Fundamental VR
GCP	Good Clinical Practice
IAPB	International Agency for the Prevention of Blindness
ICEH	International Centre for Eye Health
INO	Instituto Nacional de Oftalmología
IRO	Instituto Regional de Oftalmología
LSHTM	London School of Hygiene & Tropical Medicine
MD	Doctor of Medicine
MEd	Masters in Education
MSICS	Manual small incision cataract surgery
OASIS	Objective assessment of skills in intra-ocular surgery
OSSCAR	Ophthalmic Simulated Surgical Competency Assessment Rubric
PCR	Posterior capsule rupture
PhD	Doctor of Philosophy
PI	Principal investigator
QUB	Queen's University Belfast
RCOphth	The Royal College of Ophthalmologists, UK
SCEH	Shroff's Charity Eye Hospital
UK	United Kingdom
USA	United States of America
VA	Visual acuity
VL	Vitreous loss
VR	Virtual reality
WHO	World Health Organization

## Keywords

Virtual reality, Simulation, Surgical Education, Cataract

# General Information

## Project Title

Fundamental Virtual Reality Simulation for Manual Small Incision Cataract Surgery Validity: Evaluation, Efficacy and Acceptability Study in Bangladesh, China, Ethiopia, India, Mongolia, Togo, United Kingdom and United States of America.

## Identifying numbers

LSHTM Application Reference Number:

## Coordinating Research Institution

Orbis International

**Study Funders**

- Orbis International

## Study Summary

Title	Fundamental Virtual Reality Simulation for Manual Small Incision Cataract Surgery Validity: Evaluation, Efficacy and Acceptability Study in Bangladesh, China, Ethiopia, India, Mongolia, Togo, United Kingdom and United States of America.
Design	
Prospective Pre-Post single-masked education-intervention randomized controlled study of intense virtual reality (VR) simulation-based surgical education of ophthalmologists in Bangladesh, China, Ethiopia, India, Mongolia, Togo, UK and USA.
 
Construct validity study of assessment scores generated by the VR simulator for novices versus experts.
 
Qualitative study of face validity of VR simulator, and acceptability questionnaire survey of users.

Aims	To investigate the efficacy of intense VR simulation-based surgical education using the Orbis-FVR simulator. To examine whether it improves competence; is acceptable and has validity. To assess the construct validity of the VR simulator's assessment capacity.
Intervention	The 'intervention training' is a structured course of training using the Orbis-FVR MSICS simulator. This training is in addition to, and an enhancement of the trainees' normal current standard conventional training, and not designed to replace it.
Outcome measures	
Assessments and follow-up time points are at baseline and 1 month.
 
Primary outcome measure: mean specific simulated surgical competency assessment score at one-month post-training intervention between groups (assessed using Sim-OSSCAR) (Appendix 4).
 
Secondary outcome measures:
 

• Assessment scores generated by Orbis-FVR Simulator pre- and post-intervention.

• Step-specific analysis: mean differences in Sim-OSSCAR score for the seven interactive steps assessed (incision, tunnel, AC entry, CCC, mobilization, removal and IOL). Total possible score 14.

• Self-reported confidence ratings (10-point Likert scale) in MSICS skills, and ophthalmic surgical skills

 
Further Exploratory Analysis:
 

• Construct validity study comparing scores generated by Orbis-FVR simulator between two cohorts of novice and expert MSICS surgeons.

• Face validity study subjectively assessing a group of expert MSICS surgeons' views of the Orbis-FVR simulator as representing MSICS

• Qualitative study of the acceptability and utility of the Orbis-FVR simulator as a training or assessment tool.

Population	The VR simulation surgical training, construct and face validity studies will be conducted in ophthalmology institutions in the Americas, Europe, Africa, and Asia. Participants will have follow-up assessments in their home training or work institutions in Bangladesh, China, Ethiopia, India, Mongolia, Togo, UK and USA.
Eligibility	
Inclusion criteria for trainee:
 
 
• Trainee ophthalmologist (year 1, 2, or 3) in collaborating institution.
 
• Agree to undertake simulation procedure assessments
 
• Agree to undertake and complete the intense VR simulation training course.
 
• Performed 0 MSICS as primary surgeon and assisted or part-performed less than 10 MSICS cases
 
 
Exclusion Criteria (trainee)
 
 
• Performed 1 or more MSICS cataract surgeries as primary surgeon; and assisted or part-performed 10 or more.
 
 
Inclusion Criteria (Expert)
 
 
1. Participants in the construct validity study are two cohorts: novice MSICS surgeons having performed 0 MSICS procedures as primary surgeon and assisted in less than 10. The second cohort is expert MSICS surgeons having performed a minimum of 1,000 MSICS procedures as primary surgeon.
 
2. Participants in face validity study are expert MSICS surgeons with over 1,000 MSICS procedures performed.
 

Duration	The anticipated overall project duration is one year. The fieldwork will take about nine months.

## Executive Summary

Cataract is the leading cause of blindness, representing 35% of global blindness. There is a huge need to perform high volumes of cataract surgery globally, to tackle the backlog of cataract cases. There is a great need to train many eye surgeons safely, efficiently, effectively, and to an acceptable level of competence.

Currently, surgical training is often conducted using the traditional “apprentice model”, where a trainee observes a qualified surgeon and learns from them, and then the surgeon supervises the trainee performing surgery on a patient. We believe that this conventional model has substantial limitations and drawbacks, making surgical training less efficient and less safe. Simulation-based surgical education in cataract and glaucoma surgery has been shown to be effective in improving competence and confidence of trainee eye surgeons. However, the role of an immersive haptic virtual reality learning environment has not been established for manual small incision cataract surgery.

We will test the hypothesis that intense virtual reality (VR) simulation-based ophthalmic surgical training impacts initial acquisition of competence in key stages of MSICS. Orbis International has partnered with FundamentalVR and expert cataract surgeons to create a MSICS simulator, using virtual reality software combined with existing gaming technology. The result is a VR simulator available at a fraction of the cost of cataract surgical simulators currently on the market. We are proposing a pilot randomized multi-country study evaluating the efficacy and acceptability of the simulator training, using simulation alone. This mix method study will combine qualitative and quantitative data collection; no patients are involved.

All the training within the ‘educational intervention’ of this study will be performed using simulation. There is no testing or interventional surgical training on patients. When three anonymized and non-identifiable recordings of supervised cataract surgical procedures are video recorded (at one month), no patients are involved, and these assessments are, as for the baseline assessments, using validated artificial model eyes and assessment rubric.

The results of this study will inform the design of a future multi-center randomized-controlled clinical trial.

# Background

## Cataract and Cataract Surgery globally

Globally there are 36 million people who are blind and a further 219 million with moderate or severe vision impairment (MSVI). Cataract remains the most common cause of blindness. Approximately 80% of blindness is preventable or treatable, and 90% of the burden is in low- and middle-income countries (LMIC). Only around half of the 230,000 ophthalmologists in the world perform surgery, and regions with the greatest burden have the lowest ratios of ophthalmologists to population. One reason for having surgeons who do not perform surgery is that they are inadequately trained to perform it. For example, in India and China, consultants do not trust their novice apprentices to perform safe surgery leading to residents performing fewer than a dozen independent surgeries in their entire training. Ophthalmologists who have graduated with inadequate surgical skills find fewer opportunities to practice their skills after graduation.

The procedure of manual small-incision cataract surgery (MSICS) is the most commonly performed cataract surgery procedure in many regions of the world and is the main standard of care. It is the commonest technique of cataract surgery taught in residency training programs in South Asia. The technique uses a smaller wound compared to the older technique of sutured extra-capsular cataract extraction (ECCE). There is less post-operative astigmatism, and fewer suture-related problems for SICS versus ECCE. The surgical and visual outcomes of phacoemulsification cataract surgery and MSICS are comparable. MSICS is an appropriate, safe, and affordable technique for blindness prevention.

## Simulation in Ophthalmic Surgical Training

A recent randomized controlled trial (RCT) of intense simulation-based surgical education for MSICS using artificial eyes showed a rapid and sustained increase in competence, a 72% reduction in complication rates, and a doubling of confidence in participants. An RCT of simulation-based surgical education in glaucoma has also illustrated a rapid and sustained increase in surgical competence as well as confidence.

The use of computerized simulation models has been validated for cataract and retinal surgery. Three computerized simulators have been used for cataract surgical training in ophthalmology: the Eyesi (VRMagic Holding AG, Mannheim, Germany), MicroVisTouch (ImmersiveTouch, Chicago, USA), and PhacoVision (Melerit Medical, Linkoping, Sweden).

A simulation-based performance test and certification for phacoemulsification cataract surgery has been established for use with the Eyesi simulator. The test showed evidence of validity, and appeared to be a useful and reliable assessment tool, both for cataract procedure-specific as well as general micro-surgical skills. HelpMeSee (New York, USA) recently launched a full-immersion surgical training simulator for the use within high capacity surgical education programs for small-incision cataract surgery. This was launched in November 2020. However, the simulator is currently unavailable in full, and the cost per unit is around US\$250,000.

## Development of the Training Curriculum

**Table 1:** Training Course Curriculum & Objectives

Pre-Course	

• Study information and consent

• Video of procedure (MSICS)

• Introduction video to Orbis-FVR simulator

Course Curriculum	

• Video of procedure (MSICS)

• Surgical procedure specifics

• Orbis Fundamentals of MSICS course

• Detailed illustration of Orbis-FVR simulator and instruction course

• Intense Orbis-FVR simulator training: Course completion to minimum 5 sequential benchmarked score.

# Methodology

## Design Summary

This research program involves a prospective, single-masked education-intervention randomized controlled study of intense virtual reality (VR) simulation-based surgical education of ophthalmologists in Bangladesh, China, Ethiopia, India, Mongolia, Togo, UK and USA. Participants will be randomized, and simulation surgical competency will be assessed at baseline and 1-month between groups. Competency will be assessed at using artificial model eyes: both groups will perform three full MSICS cases using model eyes at baseline. At one-month post intervention, both groups will again perform three full MSICS using model eyes (primary outcome).

The study will assess the construct validity study of assessment scores generated by the VR simulator for novices versus experts. Both Novices and Experts will perform three full VR cases using the simulator. The first score will be disregarded to allow for familiarization with the hardware, and the mean of the second and third cases will be recorded.

Qualitative study of face validity of VR simulator, and acceptability questionnaire survey of users. An anonymous survey administered to experts and novices, using a Likert scale.

## Study Setting

This is a multi-center study. We will enroll trainee ophthalmologists (doctors who have graduated from medical school and are currently undergoing ophthalmology specialist training) in 9 ophthalmology training institutions in Bangladesh, China, Ethiopia, India, Mongolia, Togo, UK and USA.

## Study Duration

The training will be conducted during 2021 and 2022.

## Study Participants

Current trainees (between January 2021 and June 2022) in all 9 training institutions will be selected according to the inclusion and exclusion criteria.

## Inclusion / Exclusion Criteria

Orbis-FVR Training Study:

Inclusion Criteria (trainee participant)

- Trainee ophthalmologist (year 1, 2 or 3) in collaborating institution.
- Agree to undertake simulation surgical procedure assessments.
- Agree to undertake and complete the intense VR simulation training course.
- Performed 0 MSICS as primary surgeon and assisted or part-performed less than 10.

Exclusion Criteria (trainee)

- Performed 1 or more MSICS cataract surgeries as primary surgeon and assisted or part-performed 10 or more.

### Inclusion Criteria (Expert)

3. Participants in the construct validity study are two cohorts: novice MSICS surgeons having performed 0 MSICS procedures as primary surgeon and assisted in less than 10. The second cohort is expert MSICS surgeons having performed a minimum of 1000 MSICS procedures
4. Participants in face validity study are expert MSICS surgeons with over 1,000 MSICS procedures performed.

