### Course Content

- Each course will combine autonomous learning and live mentorship.
- Autonomous learning will consist of a series of 15-minute video presentations, which include:
  - Narrated demonstration video of specific VR step(s)
  - PowerPoint presentations

- Instrument use demonstrations
- Live mentorship will be delivered in two ways:
  - Local mentor who provides in-person mentorship
  - International mentor from technical advisory group provides live tele-mentorship

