## Construct Validity

Construct validity essentially assesses the sharpness of a tool, in this context addressing the question: can the simulator be used to discriminate between a novice and an expert. Mean assessment scores generated by Orbis-FundamentalVR MSICS simulator will be compared between two cohorts of surgeon: novice and expert. There will be 5 in each cohort, each performing 3 cases. The first case will be disregarded and the mean of the remaining two cases will be recorded and analyzed.

Participants in the construct validity of assessment scores will be recruited from three centers.

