## Sample size

Based on pilot and published data we anticipate the mean Sim-OSSCAR score to be 10/40 (standard deviation (SD) 6 points) at baseline. We anticipate an effect size of 2.5 SD in the mean Sim-OSSCAR between groups. We assume a correlation between these observations of 0.8. Variation between clusters (training institutions) will be accounted for with a co-efficient of variation of 0.5.

Therefore, a sample of 52 individuals in total (26 in each arm) would have 80% power and 95% confidence to detect a difference of 15 points (2.5SD). We will recruit 60 participants for the Orbis-FVR training study to provide 8 extra participants as we anticipate a moderate loss to follow-up.

We and our collaborators consider this sample size of 60 participants to be feasible within the available time and financial resources. It would take longer (an extra academic year) if we needed to recruit many more, and if the impact of COVID-19 on training continued throughout the recruitment year.

For the construct validity of the FVR assessment capacity, we will recruit a total of 5 experts and 5 novices from participating centers. Sample sizes of content, face and construct validity study are based on data from recent validation studies of ophthalmic simulation surgical competency assessment rubrics. Additionally, as we predict a large differences between the two participating groups, small cohort numbers suffice. For face validity, we will recruit ten experts from multiple centers, likewise, this was determined based on data from similar face validation studies.

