## Study Timetable:

**Figure 1.** Detailed timeline of recruitment, assessment, and training.

2021/2022:	Feb	Mar	Apr	May	Jun	Jul	Aug	Sep	Oct	Nov	Dec	Jan	Feb	Mar
Orbis research concept template	X													
Protocol development	X	X												
Collaborating institution MOUs		X	X											
Orbis-FVR simulator training course			X	X										
Equipment procurement & shipping	X	X	X	X										
Ethics submission		X	X											
Recruitment					X	X	X	X	X					
Baseline assessments					X	X	X	X	X	X				
Construct validity study (novices)					X	X	X	X	X	X				
Orbis-FVR simulator training					X	X	X	X	X	X	X			
1-month follow-up assessments						X	X	X	X	X	X	X		
Face validity study							X	X	X	X				
Construct validity study (experts)							X	X	X	X				
Qualitative / acceptability data								X	X	X	X			
Data analysis										X	X	X		
Final report													X	
Presentation & Publication													X	X

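### Prior simulator use is neither excluded nor recorded in either construct-validity cohort, so the expert-novice gap could mix device familiarity with surgical skill.

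*Combined protocol and SAP*

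**What the plan says.** **Eligibility.** Under Inclusion Criteria (Expert), one cohort is "novice MSICS surgeons having performed 0 MSICS procedures as primary surgeon and assisted in less than 10". The other is defined by volume: "The second cohort is expert MSICS surgeons having performed a minimum of 1000 MSICS procedures". The Eligibility row of the Study Summary gives the same thresholds. Neither place mentions earlier use of the simulator, mentoring on the course or a part in developing the device.

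**Source and size.** Sample size says "we will recruit a total of 5 experts and 5 novices from participating centers". Construct Validity narrows the source: "Participants in the construct validity of assessment scores will be recruited from three centers". The size is justified only in words: "as we predict a large differences between the two participating groups, small cohort numbers suffice".

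**Familiarity control.** Each person performs three simulator cases. In the Design Summary, "The first score will be disregarded to allow for familiarization with the hardware", and the mean of the second and third cases is used.

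**Baseline items.** For experts these are sex, institution and MSICS count. For trainees they are age, sex, year, institution and surgical counts. Simulator use is on neither list.

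**Who may have used the device.** The Executive Summary says that expert cataract surgeons took part in creating the simulator. Course Content lists, for each course, a "Local mentor who provides in-person mentorship".

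**Timing.** In the Study Timetable, trainee simulator training runs June to December 2021 and expert testing August to November. Novice testing runs June to November, the same months as the baseline assessments. A separate simulator training course row covers April and May.

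**The concern.** Assessing the construct validity of the simulator's score is a stated aim, and the Construct Validity section frames the question as whether the score separates novices from experts. For a difference to be read as surgical skill, the cohorts should differ in skill and not systematically in practice on the device.

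The plan itself treats practice as affecting the score: it discards a case for that reason, and it makes the simulator score before and after training a secondary outcome. Yet it does nothing to keep prior practice equal between cohorts beyond that one case. With five people per cohort, each person is 20% of the group, so one or two exposed individuals carry weight. Because exposure is not recorded, an imbalance could not be adjusted for or even reported afterwards.

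Face validity has a related gap. Its ten experts also qualify on volume alone, so a surgeon who helped build the simulator could be rating their own product.

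**Working it through.** **Is there a figure to reproduce?** No. The five-per-cohort size comes with no effect size, SD, power or named test.

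**Timing, read by column position in the timetable.** The expert window (August to November) opens two months after trainee training starts in June and lies wholly inside the June to December training period. It overlaps the novice window for four months. Exposure before testing is therefore possible for experts. The months of the novice row suggest testing around baseline, before training, but no text says so.

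**Is one discarded case enough?** It can help two groups that are both new to the device. It does not make a first-time user equal to someone who has already practised. Course delivery asks trainees for at least five full simulator cases, with a reliability gate of 3 and a minimum score of 85, so the plan does not treat one case as enough practice.

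**Size of the possible bias.** Let k be the number of exposed experts out of 5 and g the familiarity gain, in SD, that remains after the discarded case. The documents give neither. Assumed ranges: k = 1 to 3, g = 0.5 to 1.5.

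Bias in the mean gap = (k/5) × g

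- Low end: (1/5) × 0.5 = 0.1 SD
- High end: (3/5) × 1.5 = 0.9 SD

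The same formula applies to exposed novices, with the sign reversed.

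**Chance of a false positive.** Assume no skill effect on the score, normal scores with SD 1, 5 against 5, and a two-sided t-test at 0.05. The plan names no test for this comparison; 0.05 is the level it gives under Statistical analysis. Simulation with 400,000 runs per cell, k experts shifted by g:

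| Exposed experts (k) | g = 0.5 | g = 1.0 | g = 1.5 |
|---|---|---|---|
| 1 | 5% | 5% | 5% |
| 2 | 6% | 7% | 8% |
| 3 | 7% | 11% | 16% |

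**Why the inflation is limited.** When only some experts are shifted, the spread within the expert group rises as well as its mean. The expected sample variance is 1 + g² × k(5 − k)/20. For k = 3 and g = 1.5 this is 1 + 2.25 × 6/20 = 1.675. Pooled with the novices it is (1.675 + 1)/2 = 1.3375, an SD of about 1.16. The standardized gap is then 0.9/1.16 = 0.78, not 0.9. With one exposed expert, the extra spread offsets the shift and there is no inflation.

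**The case against.** The strongest reply is that exposure is inferred. No text says that a construct-validity expert will be a mentor or developer. The mentors' own MSICS volume is not stated, so they may not reach 1,000 cases. Course delivery describes facilitation, discussion and periodic checks, not mentors performing simulator cases, so substantial hands-on practice cannot be read from it. The developers are not placed at the three recruiting centers. All of this stands: the point is an uncontrolled possibility.

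The timetable covers the whole study and nine institutions, with recruitment from June to October. An expert tested in August could precede that site's first course. A reader might infer from the later window that experts will have used the device; the documents do not support that.

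The discarded first case is a genuine control, applied to both cohorts. It stands as a partial one.

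The Study Summary lists construct validity under exploratory analysis, in a study the Executive Summary calls a pilot, and sets no success threshold. The plan also predicts a large difference, so a complete absence of skill effect is a limiting case. These points reduce the weight of the concern. They do not remove it, because construct validity is a stated aim and Expected Outcomes anticipates claiming it.

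On remedy, one could argue that recording prior use would suffice. Recording permits reporting, but with five per cohort it leaves little room for adjustment, and an eligibility line costs little more.

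**Conclusion.** The gap in the plan is real: neither cohort has to be new to the simulator, prior use is not collected, and the one discarded case is a partial control. The expert-novice difference could therefore reflect familiarity as well as skill, in either direction. The documents do not show that it will.

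The size rests entirely on assumed k and g. Over the ranges used, the bias is 0.1 to 0.9 SD and the false-positive rate about 5% to 16%, with real inflation only when two or three of the five experts are exposed. A reader might treat the 0.9 SD as a shift shared by all five experts and arrive at about 24%. That does not match a scenario in which three of five are exposed.

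The randomized primary comparison is unaffected. The change is worth making now because exposure cannot be undone, or balanced between cohorts, once the cases have been recorded.

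**What to change.** - **Eligibility (Study Summary and Inclusion Criteria (Expert)).** For both construct-validity cohorts, require no use of the Orbis-FVR simulator before the three test cases. This excludes surgeons who helped develop it.
- **Timing.** Test any expert who will be a local mentor before that person's orientation to the simulator, with an earlier slot in the timetable where needed. State that novices are tested before any course.
- **Baseline Data.** Add prior simulator use to the items for trainees and for experts.
- **Face validity.** Exclude developers from the ten experts, or report their ratings separately.

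The cost is one eligibility line, one data item and a timetable note. The downside is a slightly smaller pool from which to find five experts.
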